12.6 Individual Volunteer Stopping Criteria

Volunteers who meet one or more of the following stopping criteria will receive no further doses of study vaccine but will be followed up for safety:

- Severe injection site reaction, see Appendix 1
- Severe systemic reaction, e.g. anaphylaxis, see section 14.2.1
- Persistent febrile reaction (>38.9°C and >24 hours) at the Investigator's discretion
- SAE related to the study agent

The medical safety of the volunteer is of paramount importance when discussing study continuation.

12.7 Study Stopping Criteria

A Safety Review Meeting will be convened to determine the progression of the study if any of the following scenarios occur:

- If one of the sentinel group or more than 20% of the volunteers in a cohort experience a severe site reaction.
- If one of the sentinel group or more than 20% of the volunteers in a cohort experience a severe systemic reaction.
- If one of the sentinel group or more than 20% of the volunteers in a cohort experience a persistent febrile reaction (>38.9°C and >24 hours)
- 1 or more volunteers experience a SAE related to the study agent.

13. PHARMACODYNAMIC ANALYSIS AND EXPLORATORY ASSESSMENTS

13.1 Pharmacodynamic blood sample – antibody response

Each blood sample will be approximately 20 mL in volume, to yield 2 aliquots each comprising approximately 5mL of serum. Five samples will be collected during Part A which represents approximately 100 mL of blood and 11 samples will be collected during Part B which represents approximately 220 mL of blood.

Detailed processing instructions will be included in a separate lab manual.

13.2 Streptococcus B swab – vaginal and rectal

Vaginal and rectal swabs will be performed during Part B of the study to assess colonisation by Group B streptococcus.

The vaginal swab will be performed of the lower vagina (vaginal introitus), and this will be followed by a separate swab of the rectum (by insertion of the swab through the anal sphincter). The vaginal swab will be performed without a speculum. Swabs will be kept, shipped and analysed separately.

Detailed processing instructions will be included in a separate lab manual.

13.3 Exploratory Assessments

[REDACTED]

[REDACTED]

[REDACTED]

[REDACTED]

[REDACTED]

14. ADVERSE EVENTS, SERIOUS ADVERSE EVENTS AND REPORTING

14.1 Adverse Events (AEs)

An AE is any untoward medical occurrence in a volunteer to whom a medicinal product has been administered, including occurrences which are not necessarily caused by or related to that product.

An AE can be:

- Any unfavourable and unintended sign (including reactions from overdose, abuse, incorrect use of any treatment, or interaction)
- Any new disease or exacerbation of an existing disease (e.g. increase in frequency or worsening in nature)
- Any deterioration in measurements of laboratory values or other clinical tests (e.g. ECG, vital signs or X-ray) that results in symptoms, a change in treatment, or discontinuation from the IMP
- Recurrence of an intermittent medical condition (e.g. headache) not present at baseline
- Other medical events regardless of their relationship to the IMP, such as accidents, falls and any injuries resulting from them.

AEs will be recorded from the start of the study, i.e. from the first visit to the study unit on Day 1, until the post-study medical visit.

After completion of the 12 week period following the first vaccination in Part B (i.e. after Visit 10), AEs will be recorded by the volunteer in a diary card, and only those deemed to be relevant or significant by the Investigator will be recorded in the eCRF. A relevant or significant AE will be any event that caused the patient to visit any health care professional. These events will be recorded and the Investigator will determine if the event was possibly related to the investigational product. Any event deemed serious will be processed as a SAE in the normal way and if considered related reported as a SUSAR.

14.2 Categorisation of Adverse Events

14.2.1 Intensity Classification

AEs will be classified as mild, moderate or severe according to the following criteria:

- | | |
|------------------|--|
| Mild: | Awareness of sign, symptom, or event, but easily tolerated. |
| Moderate: | Discomfort enough to cause interference with usual activity and may warrant intervention. |
| Severe: | Incapacitating with inability to do usual activities or significantly affects clinical status and warrants intervention. |

14.2.2 Causality Classification

The relationship of an AE to the study vaccine will be classified according to the following:

- Definite:** A reaction that: follows a reasonable temporal sequence from administration of the vaccine, follows a known or expected response pattern to the suspected vaccine, could not be reasonably explained by the known characteristics of the volunteer's clinical state and, if necessary, the reaction returns on re-starting the vaccine (re-challenge).
- Probable:** A reaction that: follows a reasonable temporal sequence from administration of the vaccine, follows a known or expected response pattern to the suspected vaccine and could not be reasonably explained by the known characteristics of the volunteer's clinical state.
- Possible:** A reaction that: follows a reasonable temporal sequence from administration of the vaccine and that follows a known or expected response pattern to the suspected vaccine but that could readily have been produced by a number of other factors.
- Unlikely:** A reaction that: follows a reasonable temporal sequence from administration of the vaccine, does not follow a known or expected response pattern of the suspected vaccine and could readily have been produced by a number of other factors.
- Unrelated:** A reaction that: does not follow a reasonable temporal sequence from administration of the vaccine and for which there is sufficient and conclusive information that the event is not related to the study vaccine.

AEs defined as definite, probable or possible will be reportable. AEs defined as unlikely or unrelated will not be reported. The output from the statistical analysis will be binary, related or not related.

14.3 Recording and Follow up of Adverse Events

Up to Day 85 (Visit 10), the volunteers will be instructed to spontaneously report all AEs to the site staff or Investigator as soon as possible. Any AEs observed or reported by a volunteer and/or staff up to Day 85 (Visit 10) will also be recorded in the eCRF. The Investigator will review results from the physical examinations. All new and aggravated findings, as compared with baseline, must be identified and recorded as AEs in the eCRF. In Part B, following Day 85 (Visit 10) AEs will be recorded by the volunteer in a diary card, and only relevant or significant AEs will be recorded in the eCRF.

AEs already recorded and designated as 'continuing' should be reviewed at each subsequent assessment.

For all AEs, the Investigator must obtain adequate information to determine the outcome of the AE and to assess whether it meets the criteria for classification as an SAE. For all AEs, sufficient information should be obtained by the Investigator to determine the causality of the AE (i.e. study vaccine or other illness). The Investigator is required to assess causality and record that assessment on the eCRF. Follow-up of the AE, after the date of therapy discontinuation, is required if the AE or its sequelae persist. Any AE that is still ongoing at the post-study medical visit will have an outcome of 'ongoing' recorded in the eCRF,

however the Investigator will continue to follow up ongoing related AEs and record information in the source documents. Related SAEs will be followed until the event resolves or the event or sequelae stabilise and this information will be reported to the Sponsor using the SAE reporting forms.

14.4 Serious Adverse Events and Suspected Unexpected Serious Adverse Reactions (SUSARs)

A SAE is any AE that:

- results in death
- is life-threatening
- requires inpatient hospitalisation or prolongation of existing hospitalisation
- results in persistent or significant disability or incapacity
- consists of a congenital anomaly or birth defect.

Important medical events that may not be immediately life-threatening or result in death or hospitalisation but may jeopardise the patient or may require intervention to prevent one of the other outcomes listed in the definition above should also be considered serious.

A SUSAR is an adverse reaction, which is both serious and unexpected.

14.5 Reporting Timelines

14.5.1 SAE Reporting

An SAE must be reported immediately (within 24 hours), independent of the circumstances or suspected cause, if it occurs or comes to the attention of the Investigator at any time during the study period. Any SAE with a suspected causal relationship to the IMP occurring at any other time after completion of the study must be promptly reported.

Contact Details for SAE Reporting:

The following mandatory information must be provided to the Sponsor pharmacovigilance contact within 24 hours for each SAE:

- Protocol number
- Volunteer number
- AE
- IMP
- Investigator's name and contact details

Causality assessment should be completed as soon as possible.

Follow-up information should be actively sought until the SAE has resolved or sequelae have stabilised. Additional information e.g. hospital reports or death certificates, may be requested by the Sponsor and should be anonymised/pseudonymised before transmission and subsequently filed in the Investigator Site File.

The expectedness of an SAE shall be determined by the Sponsor according to the most recent version of the Investigator's Brochure.

14.5.2 SUSAR Reporting

The Sponsor shall ensure that all relevant information about a suspected unexpected serious adverse reaction (SUSAR), which occurs during the course of a clinical trial in the United Kingdom and is fatal or life-threatening is reported as soon as possible to the MHRA, the competent authorities of any EEA State, other than the United Kingdom, in which the trial is being conducted, and the relevant Ethics Committee. This needs to be done not later than seven days after the sponsor was first aware of the reaction. Any additional relevant information should be sent within eight days of the report.

A sponsor shall ensure that a SUSAR which is not fatal or life-threatening is reported as soon as possible and in any event not later than 15 days after the sponsor is first aware of the reaction.

14.6 Abnormal Findings from Investigations or Assessments

Abnormal findings from investigations or assessments will be recorded as AEs if the Investigator considers they are clinically significant and/or result in medical intervention. This may include but is not limited to abnormal laboratory results, physical examination findings, ECG values/changes and vital sign values/changes.

14.7 Pregnancy

Pregnancy is not an adverse event but the outcome of a pregnancy might be an adverse event. Over the course of the 1 year follow up period in Part B it is possible that one or more volunteers may become pregnant. It is important that any pregnancy is followed up. On being notified of a pregnancy the Investigator will complete a pregnancy notification form, which will be submitted to Diamond Pharma Services, and will inform the Sponsor. Diamond Pharma Services will seek permission to follow up the pregnancy and at the time of the estimated date of delivery will contact the Investigator to remind the Investigator to determine the outcome of the pregnancy with the volunteer.

In the event of a pregnancy occurring during the course of the study, and with the written consent of the pregnant woman (under a separate consent form), matched serum samples from the mother and cord blood will be collected and relevant serum analyses will be performed at the University of Lund as described under the exploratory assessments.

15. STATISTICAL EVALUATION

Details of the planned statistical analyses will be described in the Statistical Analysis Plan (SAP) and some important features are presented in this protocol. Statistical analyses will be performed by Eurofins Optimed using SAS statistical software.

15.1 Statistical method description

15.1.1 General information

Statistical results will be separately presented for parts A and B.

Demographic, baseline characteristics and data recorded during the study will be summarised using descriptive statistics by treatment (placebo, vaccine taken alone or vaccine combined with adjuvant) and dose group, unless otherwise specified. If relevant additional descriptive graphs can be provided.

Individual data for all included volunteers will be presented as a data listing, sorted by treatment and administered dose level.

For parameters with evaluation before vaccination and in case of re-checked value(s), only the last observation prior to dosing will be used in descriptive and inferential statistics and derivations of other parameter values. After vaccination, only values of scheduled assessments (planned in the protocol) will be used.

For laboratory/clinical parameters for which laboratory/reference ranges will be available, position of parameter values according to ranges will be flagged with the following rule:

- "L" for values lower than laboratory/reference ranges;
- "H" for values higher than laboratory/reference ranges.

In addition, parameter values can be assessed by investigator and flagged as follows in order to determine clinical relevance:

- Normal;
- Abnormal and NCS (Not clinically Significant);
- Abnormal and CS (Clinically Significant).

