Given that GBS-NN has been found to be [REDACTED] protect against infections with serotypes Ia, Ib, II, III and V. And taken together with the finding that high levels of naturally occurring antibodies against Rib and AlphaC [REDACTED] correlate with protection against invasive GBS disease in newborns, makes GBS-NN an ideal candidate for a GSB vaccine with an estimated coverage of 95% of clinical isolates and hence justifies clinical testing of the vaccine.

[REDACTED]

Based on the data derived from the dose ranging studies in mice, it is considered appropriate to commence dosing at 10µg in humans.

The present study will also investigate whether adding the adjuvant Aluminium hydroxide (Alhydrogel®) will improve the immune response, and this will be done in parallel with dosing of GBS-NN.

It is anticipated that dose escalation will occur with a five-fold increment. Dose escalation will only occur after review of safety data up to two weeks after vaccination. At this review a decision will also be made whether a booster dose is required (may be given 28 days after first vaccination).

In Part A, the first cohort will consist of 10 volunteers (8 active, 2 placebo) to receive a dose of 10µg without Alhydrogel®, the second and third cohorts may be dosed in parallel. Cohort 2 will receive a dose of 50µg, without Alhydrogel® and cohort 3 will receive 10µg GBS-NN with Alhydrogel®. Cohorts 4 and 5 may also be dosed in parallel with 250 µg without Alhydrogel® in cohort 4, whilst cohort 5 will receive 50µg with Alhydrogel®. The 6th cohort will receive 250µg GBS-NN with Alhydrogel®.

It is anticipated that the results from Part A will reveal where the optimal dose is likely to lie, and three dose regimens will be selected for evaluation in Part B. In Part B, each cohort will consist of 80 volunteers (60 active, 20 placebo)

It is expected that data accrued from the present study will allow the selection of the most appropriate dose to elicit the best immune response in humans. This dose will then be tested in pregnant women in subsequent studies with an expectation of 95% cover of GBS serotypes compared with 70% achieved with other vaccines.

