The normal adverse event profiles from Phase I studies suggest that a typical array of minor clinical study symptoms may be experienced by volunteers taking part in the study. GBS-NN has not previously been tested in human volunteers, although it is known that naturally occurring antibodies, reactive against the GBS-NN are found in pregnant women; the possibility of as yet unknown side effects should remain a consideration. The protocol requires that volunteers are monitored after vaccine administration (vital signs and general signs and symptoms), with regular follow-up visits for physician assessment and questioning regarding AEs will be conducted for all volunteers in the study. GBS-NN, like other protein-based vaccines, may theoretically be associated with a transient febrile reaction (body temperature greater than 38.0°C but not greater than 38.7°C) following vaccination. Immune complex-mediated reactions are unlikely given the recombinant nature of GBS-NN, however, it is still possible that hypersensitivity may occur.

Based on the results from clinical use of other protein vaccines adsorbed to Alhydrogel®, and other aluminium containing adjuvants transient local reactions at the injection site, including pain, oedema, bruising, erythema and induration, mainly of mild intensity, are likely to occur. In addition flu-like symptoms, such as fatigue, malaise, myalgia, and mild to moderate headache may occur.

GBS-NN vaccination is contraindicated in volunteers known to suffer hypersensitivity reactions to vaccines or a known allergy to aluminium hydroxide. For the purpose of the study volunteers who have experienced a significant illness in the four weeks prior to check in will be excluded. The vaccine should not be given to volunteers with known or suspected immune deficiency, autoimmune diseases or who have an acute infection.

GBS-NN should not currently be given to women known, or suspected to be, pregnant, or to nursing mothers. Currently GBS-NN should only be administered to women of child-bearing potential if adequate contraceptive precautions are taken, accompanied by serum and/or urine pregnancy testing prior to vaccination and during follow up.

All study volunteers will be monitored for potential side effects of vaccination during the entire course of the study, as per the protocol, and adverse events must be appropriately followed up.

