10. INVESTIGATIONAL MEDICINAL PRODUCT

10.1 Identity and Doses of IMP

The GBS-NN vaccine will be supplied [REDACTED]

[REDACTED]

[REDACTED]

[REDACTED]

[REDACTED]

In Part A, GBS-NN will be administered with and without Alhydrogel® (see table below for anticipated dose regimens). Cohorts in Part B may also receive GBS-NN without Alhydrogel® depending on the dosing regimens chosen. The procedure for the assembly of the different dose levels for Part A of the study is described in detail in the Pharmacy Procedure “Assembly of GBS-NN and placebo doses”. This procedure will be followed and, if required, amended to allow the assembly of additional dose strengths if indicated in Part B.

[REDACTED]

Individual volunteer treatments will be dispensed by the [REDACTED] pharmacist and labelled in accordance with Annex 13 of “The Rules Governing Medical Products in European Community, volume 4 Good Manufacturing Practice for Medicinal Products”.

The placebo vaccine [REDACTED]

[REDACTED]

It is currently anticipated that the following dosing strategy will be employed, however this may be modified, see below.

Part A:

Three dose levels will be selected, with and without Alhydrogel®: A, B, and C (where A is the lowest dose and C is the highest dose). It is anticipated that these doses will be 10µg, 50µg and 250µg, although these may be modified following ongoing review of data by the Safety Review Committee. The dose increase between cohorts will not exceed a five-fold increase.

It is anticipated that each cohort will receive the following dose regimen as described in the table below.

Note that cohort 7 is an optional cohort, and will proceed if deemed necessary to test an additional dosing regimen at a dose level below 250 µg, which will be determined following an ongoing review of the data.

Cohort	Dose schedule	Dose level	Adjuvant
1	Day 1, 29	10µg (A)	None
2	Day 1, 29	50µg (B)	None
3	Day 1, 29	10µg (A)	Alhydrogel®
4	Day 1, 29	250µg (C)	None
5	Day 1, 29	50µg (B)	Alhydrogel®
6	Day 1, 29	250µg (C)	Alhydrogel®
7	TBD	TBD, not exceeding 250 µg	TBD

Anticipated dose regimens in Part A

The aim of the dose finding overall is to identify the minimum dose level which provides the maximum immune response in terms of seroconversion rate, level of specific IgG reached and shortest time to peak level, whilst maintaining an acceptable safety profile.

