12.2 Treatment Period and Post-Study Period

12.2.1 Part A

Volunteers will receive one of up to 7 dosing regimens of GBS-NN or placebo on 1 or 2 occasions – a primary dose will be administered at Visit 2 and volunteers will remain in the study unit for at least 8 hours post-dose, and if a booster dose is required, this will be administered at Visit 6. There will be a time interval of 4 weeks between Visit 2 and Visit 6, although this time interval may change if the dosing regimen is changed. There will be 10 volunteers in each group, 8 randomised to active and 2 to placebo. All cohorts in Part A will incorporate sentinel dosing of 2 volunteers in each cohort for the primary dose only: 1 on active treatment and 1 on placebo. No further volunteers in that cohort will be dosed until at least 24 hours after dosing the second volunteer, provided that there are no serious or unexplained safety issues as determined by the Investigator.

The decision to proceed with administration of the primary dose in subsequent cohorts will be made as described in Section 12.5.

The following assessments will be carried out at these visits:

Visit 2

A urine pregnancy test, brief physical examination, urine drugs of abuse test and alcohol breath test will be performed to confirm eligibility. Eligible volunteers will be randomised to receive active or placebo on 1 or 2 occasions (all volunteers will receive a primary dose at Visit 2 and a booster dose of the same medication (active or placebo) will be administered at Visit 6 if required). The dose administered, the number of doses and the time interval between doses will be dependent on the data generated from the preceding cohort and will be decided by the Safety Review Committee. A pharmacodynamic blood sample will be taken to measure pre-existing antibody levels prior to dosing. The primary dose will be administered at Visit 2 and volunteers will remain in the study unit for at least 8 hours post-dose. Vital signs will be recorded pre-dose and at 2 and 6 hours post-dose. A brief medical examination (including an assessment of the injection site) will be performed prior to discharge to ensure the volunteer is fit for discharge.

Visit 3

Visit 3 will be performed 24 hours (\pm 2 hours) after administration of the primary dose and an assessment of the injection site will be performed, vital signs will be recorded and AEs and concomitant medications will be reviewed.

Visit 4

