15.1.3 Inferential statistics

Adequate statistical tests will be used to carry out comparison between treatment/dose groups performed on primary, secondary or exploratory endpoints, even though it is accepted that the power of these tests for groups in Part A will be low due to small numbers of volunteers.

For categorical endpoints, such as local and systemic reactogenicity, a comparison of events intensity (scores) between vaccine dose groups will be performed with an adequate statistical test dealing with categorical variables (for example: Fisher exact test, Chi square test or generalized estimating equations).

For continuous endpoints, such as immune response induced by different GBS-NN vaccine dosing regimens, appropriate statistical method (for example: ANOVA) will be used to compare pre-vaccination and post-vaccination levels.

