15.4.2 Primary endpoint for the two study parts

The primary objective is to evaluate the safety and tolerability of the GBS-NN vaccine for 12 weeks after the first dose of vaccine.

All the included volunteers (including the withdrawal and dropout volunteers) will be evaluated for safety analysis (ITT).

The following endpoints will be evaluated:

- **Local and systemic reactogenicity**

Assessment results will be described according to treatment/dose group and visit.

- **Adverse events**

Adverse events will be coded according to the Medical Dictionary for Regulatory Activity (MedDRA). They will be classified into pre-defined standard categories according to chronological criteria:

- Treatment Emergent Adverse Events (TEAEs): AEs which occur for the first time after the first administration or present before and worsened during vaccine exposure;
- Non-Treatment Emergent Adverse Events (NTEAEs): AEs which occur before the first study vaccine administration (also called "pre-dose event").

TEAEs will be described by relation to study vaccine (for example: definite / probable / possible / unlikely / unrelated) and maximum intensity (for example: mild / moderate / severe) according to treatment/dose group. Descriptive statistics will be characterised by number of TEAEs, number and percentage of volunteers with at least one TEAE (based on ITT). In case of few TEAEs (≤ 5 per study part for example), only a listing will be performed.

Vaccine related TEAEs (*i.e.* definite, probable or possible relationship to study vaccine) will be summarised by MedDRA codes (SOC and PT) and treatment/dose group. In case of few vaccine related TEAEs (≤ 5 per study part for example), only a listing will be performed. TEAEs not related to study vaccine (*i.e.* unlikely or unrelated relationship to study vaccine) will also be summarized by MedDRA codes.

Two distinct listings of TEAEs and NTEAEs will be presented by treatment/dose group, volunteer and MedDRA codes in order to provide more information about adverse events (example: description, duration, time since last administration if applicable, seriousness, any actions taken as concomitant medication or hospitalization).

- **Laboratory tests**

Biochemistry and haematology tests will be performed at V1 (screening), V4 (part A), V5 (part B), V8 (parts A and B) and post-study medical visit (V10 for part A and V20 for part B).

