* For Part A the threshold to define a positive response will be set arbitrarily to 2.5-fold rise above base-line, as is common practice in FIM vaccine studies. For Part B, the threshold will be set based upon the data derived from Part A. The fold increase for all 12 placebo recipients at Days 29, 43, 57 & 85 will be considered. The mean and standard deviation will be calculated and the cut-off defined as two standard deviations above the mean.

The primary immunological endpoints (still secondary study endpoint) for both Part A and Part B will be the values of these endpoints at Day 85, 12 weeks after the administration of the first dose of vaccine).

In Part A, the immunological endpoints at Days 1, 29 and 57 will be reported separately by group in a blinded fashion to enable the dose selection for Part B

Additional analyses to address objectives

For each group the individual data will be presented as scatter plots and cumulative frequency distributions at each time-point

Correlation plots will be generated to compare the specific antibody concentrations before vaccination and at 12 weeks after the first dose to evaluate the influence of pre-existing antibody levels on responses.

Statistical significance of differences in endpoint values

Statistical tests will be carried out to compare results between treatment groups, depending on studied variable type (see section inferential statistics). These analyses will be fully detailed in the SAP. In brief the following comparisons between groups will be made at Day 29 and Day 84 (and at Day 57 in Part A only):

Part A:

- Placebo group (total 12 volunteers, 6 with buffer only and 6 with alhydrogel) against all other dose groups
- Each dose level with and without Alhydrogel®
- 10µg vs 50µg, 10µg vs 250µg, 50µg vs 250µg in volunteers vaccinated with GBS-NN alone
- 10µg vs 50µg, 10µg vs 250µg, 50µg vs 250µg in volunteers vaccinated with GBS-NN in the presence of Alhydrogel
- For all groups and parameters Day 29 vs Day 85

Part B:

- Placebo group against all other dose groups (regimens to be decided)
- Group A vs Group B; Group A vs Group C; Group B vs GroupC
- For all groups and parameters Day 29 vs Day 85

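### Part A safety tables: the default summary splits vaccine by adjuvant but names one placebo category, so buffer and Alhydrogel placebo recipients would share a column

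*Combined protocol and SAP*

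**What the plan says.** Section 15.1.1 of the combined protocol and SAP sets the default layout: data are to be "summarised using descriptive statistics by treatment (placebo, vaccine taken alone or vaccine combined with adjuvant) and dose group, unless otherwise specified". That gives two vaccine categories, by adjuvant, and one placebo category.

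Section 15.4.2, which covers the primary safety endpoint, says of local and systemic reactogenicity: "Assessment results will be described according to treatment/dose group and visit". Adverse events are also laid out by treatment/dose group. Neither paragraph says how placebo is to be displayed.

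The make-up of the placebo group appears in 15.4.4, among the antibody comparisons: "Placebo group (total 12 volunteers, 6 with buffer only and 6 with alhydrogel) against all other dose groups". It agrees with the allocation in 12.2.1 ("There will be 10 volunteers in each group, 8 randomised to active and 2 to placebo") and with the cohort table in 10.1.

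On expected reactions, 6.3 begins "Based on the results from clinical use of other protein vaccines adsorbed to Alhydrogel®, and other aluminium containing adjuvants transient local reactions" and goes on to call such reactions likely and mainly mild.

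**The concern.** Safety and tolerability is the primary objective, and local reactogenicity is the first endpoint listed under it. Part A gives GBS-NN both plain and with Alhydrogel, and by the count in 15.4.4 half of the planned placebo recipients receive Alhydrogel. Each vaccine formulation therefore has a matching placebo, and the default table would merge the two.

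Suppose Alhydrogel without antigen causes more local reactions than buffer. The pooled placebo rate then lies between the two. Beside plain GBS-NN it is too high, so the excess over placebo looks too small. Beside adjuvanted GBS-NN it is too low, so part of what the adjuvant does looks like an effect of the antigen. The risk is to how the descriptive tables are read, and only if the two placebos really differ.

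**Working it through.** **Placebo count.** Inputs: 8 active and 2 placebo per cohort (12.2.1); cohorts 1, 2 and 4 without adjuvant, cohorts 3, 5 and 6 with Alhydrogel (table in 10.1).

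- Buffer placebo: 3 × 2 = 6. Alhydrogel placebo: 3 × 2 = 6. Total 12, which reproduces 15.4.4 exactly.
- Active: 3 × 8 = 24 plain and 24 adjuvanted, 8 at each dose.
- Section 10.1 adds: "Note that cohort 7 is an optional cohort". Its adjuvant is still to be decided. If it runs, the total becomes 14, split 8 and 6 or 6 and 8.

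**Error in the pooled rate.** With p_b the buffer rate, p_a the Alhydrogel rate and 6 women on each, the pooled expectation is (p_b + p_a)/2. It differs from either matching rate by (p_a − p_b)/2. The documents give no rates, so these are assumptions:

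- 10% and 10%: pooled 10%, error 0.
- 10% and 30%: pooled 20%, error 10 points each way.
- 10% and 50%: pooled 30%, error 20 points each way.

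**Bias against precision.** Splitting removes the bias but halves the number per column. The root mean square error (RMSE) against the matching placebo rate is:

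- pooled: √{[6p_b(1−p_b) + 6p_a(1−p_a)]/144 + [(p_a−p_b)/2]²}
- split: √{p(1−p)/6} for each formulation, with p its own rate

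| Assumed buffer / Alhydrogel | Pooled RMSE | Split, buffer | Split, Alhydrogel | Split, averaged over both |
|---|---|---|---|---|
| 10% / 10% | 8.7 points | 12.2 | 12.2 | 12.2 |
| 10% / 30% | 15.0 | 12.2 | 18.7 | 15.8 |
| 10% / 50% | 23.3 | 12.2 | 20.4 | 16.8 |

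The last column is the root of the mean of the two squared errors; for 10%/30% it is √[(0.015 + 0.035)/2] = 0.158. With 10% for buffer, splitting is better overall only when the gap exceeds about 23 points, from (p_a − p_b)² = [p_b(1−p_b) + p_a(1−p_a)]/6.

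**Precision when no events are seen.** The exact two-sided 95% upper limit is 1 − 0.025^(1/n): 46% for 0/6 and 26% for 0/12.

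**Effect on a test, if one were run.** Section 15.1.3 opens by allowing tests between treatment/dose groups on primary endpoints. I enumerated all outcomes for a two-sided Fisher test at p ≤ 0.05, with 8 vaccinees in one dose group and no antigen effect:

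| Comparison | 10% / 30% | 10% / 50% |
|---|---|---|
| Adjuvanted vs pooled 12 | 4.5% | 7.0% |
| Adjuvanted vs 6 Alhydrogel placebo | 1.4% | 2.0% |
| Plain vs pooled 12 | 0.9% | 4.1% |
| Plain vs 6 buffer placebo | 0.1% | 0.1% |

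Pooling moves these rates little in absolute terms. Power within formulation is low: for 8 plain vaccinees against 6 buffer placebos it is 3% for 30% vs 10% and 21% for 50% vs 10%.

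**The case against.** The strongest reply is that 15.1.1 is only a default. It carries its own exception clause, section 15 leaves details to the SAP, and table columns are usually settled there. The description of the placebo in 10.1 is blacked out, which is no fault of the plan. All this stands, and a reader should not infer that the plan explicitly pools placebo for safety: the explicit single group is in the antibody comparisons. But nothing in the combined document specifies a split, so the default is what a programmer would follow. Reading the reference to dose group as a split of placebo by cohort does not help, because placebo has no dose level and 15.4.4 treats it as one group.

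Second, pooling may be a sensible trade of bias for precision. That also stands: averaged over both formulations, pooling is the more accurate in two of the three scenarios above. It argues for keeping the pooled column, but not for showing it alone.

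Third, a reader might infer from 6.3 that Alhydrogel placebo is expected to react more than buffer. The text does not say so. It concerns vaccines adsorbed to aluminium adjuvants, not adjuvant without antigen, so a difference is plausible but unsupported by any figure.

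Fourth, the tables already show plain and adjuvanted vaccine separately at each dose, 8 against 8, and individual data are listed. The plain-versus-adjuvanted contrast is therefore intact. Listings are not a matched placebo rate, however.

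**Conclusion.** The point holds as a gap in table specification, limited to the descriptive Part A reactogenicity and adverse event tables. As written, buffer and Alhydrogel placebo recipients would share one column. The distortion is half the difference between their reaction rates: 10 to 20 points each way under the assumed 10% versus 30% to 50%, and nothing if the rates are equal. The 6 and 6 assume that cohorts 1 to 6 run as planned; 8.1 and 12.5 allow only one of cohorts 4 and 5 to proceed, 9.6 provides for replacements, and cohort 7 is open.

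A reader might infer that the primary safety analysis or the safety decisions are biased. The documents do not support that. The reactogenicity test named in 15.1.3 is "a comparison of events intensity (scores) between vaccine dose groups will be performed with an adequate statistical test", which does not involve placebo. Escalation (12.5) and the study stopping rules (12.7) do not rest on a vaccine-versus-placebo comparison. Nor does it follow that the pooled column is wrong or that tests within formulation are needed. This is a worthwhile but optional change.

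**What to change.** In 15.1.1 and 15.4.2, or in the SAP, add a sentence: Part A reactogenicity and adverse event tables show placebo by the formulation actually received (buffer or Alhydrogel) beside the matching vaccine groups, in addition to the pooled placebo column. Use counts as observed, including replacements and any cohort 7 placebo recipients placed by their formulation, and write no fixed n into the text. Label the columns descriptive, do not require tests within formulation, and leave the pooled placebo group for the antibody comparisons unchanged.

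The cost is at most two extra columns from data already collected. Each split column will be imprecise, as the exact limits above show, and should be read with the pooled column.
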